This is a Phase 3, multicenter, randomized, double-blind, placebo-controlled efficacy and safety study designed to compare tofacitinib to placebo in subjects with active AS. An estimate of approximately 480 AS subjects will be screened globally in order that approximately 240 eligible subjects (120 per arm) will be randomized in a 1:1 ratio to tofacitinib 5 mg BID (twice daily) or matching placebo BID. Active disease is required for entry into this study and is defined as: Modified New York Criteria for Ankylosing Spondylitis (1984), Bath Ankylosing Spondylitis Disease Activity Index (BASDAI) score of ≥ 4 and back pain score (BASDAI Question 2) of ≥ 4 despite an adequate therapeutic trial with 2 or more non-steroidal anti-inflammatory drugs (NSAIDs) (or intolerance to NSAIDs).

Eligible subjects will be treated with one of the two sequences for 16 weeks followed by treatment with tofacitinib 5 mg BID for an additional 32 weeks.

The duration of participation for eligible subjects will be approximately 56 weeks. This will include a screening period of approximately 30 days, a 16-week double-blind treatment period, a 32-week open-label treatment period and a 28 day follow-up period. During the 16-week treatment period subjects will visit the clinic every two weeks (± 3 days) until the Week 4 visit and then every 4 weeks (± 7 days) until completion of Week 16. At the Week 16 visit all subjects will be assigned to open-label tofacitinib and will visit the clinic every two months (± 7 days) until week 48. Subjects will then return to the clinic for a Follow-up visit approximately 28 days after the week 48 visit. The investigators, subjects and sponsor study team will remain blinded to the first 16 weeks of treatment assignment through the entire duration of the trial until database release.

Amendment 3

All subjects in the study will be evaluated for risk factors for venous thromboembolism (VTE) (2019 ESC guidelines for the diagnosis and management of acute pulmonary embolism developed in collaboration with the ERS. European Heart Journal (2020) 41;543-603).

The study investigator or designee will need to review each subject's medical history and study records, including their concomitant medications, to determine whether he/she is at high risk for developing VTE.

A subject may be at high risk for VTE if he/she:

- has heart failure or prior myocardial infarction within the past 3 months;
- has inherited coagulation disorders;

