- has had VTE, either deep venous thrombosis or pulmonary embolism;
- is taking combined hormonal contraceptives or hormone replacement therapy;

- has a malignancy (association is strongest with cancers other than non-melanoma skin cancers);
- is undergoing major surgery or is immobilized.

Additional risk factors for VTE, such as age, diabetes, obesity (body mass index [BMI] ≥ 30 kg/m²), smoking status, hypertension, and first degree family history of VTE should also be taken into consideration by the investigator and the sponsor medical monitor when evaluating the benefit:risk for each individual subject whether to discontinue from open-label 5 mg BID dose of tofacitinib.

See Risk Factor Check for VTE in Section 7.1.14 for tofacitinib dosing guidance when a risk factor is identified.

If a subject has 1 or more of the risk factors for VTE listed above and is receiving tofacitinib 5 mg BID, they may remain on tofacitinib 5 mg BID after careful investigator assessment of benefit: risk. For subjects who do not have any of the risk factors for VTE listed above, he/she will remain on their open-label tofacitinib dose of 5 mg BID.

Study Treatments

Subjects will be randomized at the Baseline visit in a 1:1 ratio to one of the following two treatment sequences for a total of 16 weeks of treatment. Randomization will be stratified by prior treatment history: (1) Biological disease-modifying anti-rheumatic drug-naïve (bDMARD-naïve) and (2) Tumor Necrosis Factor inhibitor inadequate responders (TNFi-IR) or bDMARD use (non-IR).

Strata (Patient Population)	Sequence	Treatment Sequence and Description	Planned Number of Randomized Subjects
bDMARD-naïve	1	Blinded Tofacitinib 5 mg BID for 16 weeks followed by open-label tofacitinib for 32 weeks One-tofacitinib 5 mg tablet in AM & PM	96
bDMARD-naïve	2	Placebo BID for 16 weeks followed by open-label 5 mg BID tofacitinib for 32 weeks One-5 mg matching placebo tablet in AM & PM for the first 16 weeks followed by one-tofacitinib 5 mg tablet in the AM & PM for 32 weeks	96
TNFi-IR or bDMARD use (non-IR)	1	Blinded Tofacitinib 5 mg BID for 16 weeks followed by open-label tofacitinib for 32 weeks One-tofacitinib 5 mg tablet in AM & PM	24

Strata (Patient Population)	Sequence	Treatment Sequence and Description	Planned Number of Randomized Subjects

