TNFi-IR or bDMARD use (non-IR)	2	Placebo BID for 16 weeks followed by open-label 5 mg BID tofacitinib for 32 weeks One-5 mg matching placebo tablet in AM & PM for the first 16 weeks followed by One-tofacitinib 5 mg tablet in the AM & PM for 32 weeks	24

Subjects will receive one tablet in the morning and one tablet in the evening for a total of two tablets per day. Placebo tablets will match the 5 mg tablets in order to maintain the blind.

At the end of the 16 week double-blinded treatment period, all subjects will be assigned to open-label tofacitinib 5 mg BID to Week 48. The investigators, subjects and sponsor study team will remain blinded to the first 16 weeks of treatment assignment through the entire duration of the trial until database release.

Statistical Methods

The Assessment of the SpondyloArthritis International Society $\geq 20\%$ improvement (ASAS20) response rate at Week 16 is the primary efficacy endpoint in this trial. The analysis of the primary endpoint will be based on the full analysis set. The normal approximation for the difference in binomial proportions adjusting for the prior treatment history at randomization (bDMARD-naïve vs TNFi-IR) via the Cochran–Mantel–Haenszel approach will be used to estimate the treatment effect (treatment difference, standard error, 95% confidence interval) and to test (Normal Z-test) the superiority of tofacitinib to placebo.

Approximately 120 subjects per arm will be randomized. A sample size of 120 per arm will yield about 89% power to detect a difference of at least 20% between tofacitinib 5 mg BID and placebo at a two-sided significance level of 5%, assuming a placebo response rate of 40% for ASAS20 response at Week 16.

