4 (17 Dec 2019)	2 (10 April 2019)	Revision to provide additional clarification after study's blinded data review.	
1. Corrected typo to remove Week 2 for endpoint of MASES as it is not assessed at Week 2 per protocol (Section 3.2.2, Section 6.3, Section 9.8 Table 8);
 
2. Clarified Tier-2 adverse events in Section 3.5;
 
3. Clarified the handling of a case when a subject has an assessment prior to or on the date of the investigational product discontinuation in the same visit window as the discontinuation (see Section 9.4, Table 5), this assessment will be considered as on-drug and used in the analysis for that visit window (Section 5.3);
 
4. Removed adverse event analyses for the incremental period: Week 16 to Week 48 as

			
analyses for Baseline to Week 16 and Baseline to Week 48 are sufficient (Section 6.6.1);
 
5. Clarified the handling of LLOQ for hsCRP is applicable to all efficacy and safety analyses, not just ASDAS_{CRP} (Section 9.2.4);
 
6. Clarified the treatment switch date as the start date from the first entry of dosing log for the period between Week 16 to Week 24 (Section 9.4, Table 5);
 
7. Removed Metamizole Sodium from the NSAID list as it is confirmed as an analgesic (Section 9.6, Table 7);
 
8. Corrected typographical errors throughout the SAP.

--	--	--	--

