5.2. General Methods

As subjects randomized to treatment group of placebo → tofacitinib 5 mg BID (ie, → means switching to) will advance from placebo to open-label treatment of tofacitinib 5 mg BID at Week 16, the treatment label used for reporting visits up to Week 16 will be “Placebo” and treatment label for reporting visits after Week 16 through Week 48 will be “Placebo → Tofacitinib 5 mg BID”. For analyses through Week 16, the following treatment comparison will be made at each time point, where applicable:

- Tofacitinib 5 mg BID vs. Placebo.

For analyses after Week 16 through Week 48, the following treatment comparison will be made at each time point,

- Tofacitinib 5 mg BID vs. Placebo → Tofacitinib 5 mg BID.

The primary efficacy comparison for the primary endpoint of ASAS20 will be between tofacitinib 5 mg BID and placebo at Week 16.

Descriptive Summaries

In general, the data for all continuous endpoints will be summarized by treatment group (ie, 2 groups) and by time point in tables containing descriptive statistics (N [which is the number of subjects evaluable for the endpoint at the time point], mean, standard deviation, standard error of the mean, minimum, 1st, 2nd (ie, median) and 3rd quartiles and maximum) for actual and change from Baseline (or percent change from Baseline) values for those endpoints measured at Baseline. In case when N=1 (ie, only one subject is

available/evaluable for summary), standard deviation and standard error will be reported as “NA” (not applicable) while the remaining statistical parameters will have the same value as the mean. The data for all response-type endpoints will be summarized by treatment group and by time point in tables showing descriptive statistics: N, n (ie, number of responders), response rate (%), standard error of the response rate, and 95% confidence interval (CI) based on normal approximation. If \hat{p} is the estimated response rate, then the 95% CI is calculated as:

$$\hat{p} \pm z_{0.975} \sqrt{\frac{\hat{p}(1 - \hat{p})}{N}}$$

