6.6.1. Adverse Events

AEs will be reported as treatment-emergent all causality and treatment-emergent treatment-related. A treatment-emergent AE is any event that starts on or after the first dosing day. The algorithm will not consider any events that start prior to the first dose date.

The relationship to study treatment is assessed by the investigator.

AEs will be displayed by two analysis periods: (1) Baseline to Week 16; and (2) Baseline to Week 48 (end of study including follow-up).

Tier-1 events, ie, AEs of special interest will be summarized descriptively.

Tier-2 events will be analyzed using asymptotic methods proposed by Miettinen and Nurminen (1985).¹¹ Risk ratios (tofacitinib 5 mg BID compared to placebo) and 2-sided 95% CI will be reported. P-values will not be reported for Tier-2 events. This analysis is applicable for the period of Baseline to Week 16 only.

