9.4. Definition and Use of Visit Windows in Reporting

For reporting purposes, the following visit windows will be used for efficacy, patient-reported outcomes and safety display that show by scheduled visits. If two or more observations fall into the same visit window, the observation closest to the target day will be used in the analyses. If there is a tie, the later observation will be used. However, for a subject who discontinues from the study early prior to the Week 48 visit and who does not have an observation within the Week 48 visit window, if two or more observations fall in the same visit window (ie, a visit window prior to Week 48), then the latest observation (rather than the observation closest to the target day) within this visit window will be used in the analysis for that visit window.

The visit windows will be applied to on-drug data and on-study data separately (see [Section 9.1](#)).

Table 5. Visit Windowing

Visit Label	Target Day ^a	Window Definition
Screening		< Day 1
Baseline	Day 1	Last non-missing assessment on or before Day 1 and prior to first dose of investigational product (ie, tofacitinib or placebo)
Week 2	Day 15	Day 2 to Day 21
Week 4	Day 29	Day 22 to Day 42
Week 8	Day 57	Day 43 to Day 70
Week 12	Day 85	Day 71 to Day 98
Week 16 ^c	Day 113	Day 99 to [Treatment Switch Day ^b or Day 140, whichever is smaller]
Week 24	Day 169	[Treatment Switch Day ^b +1 or Day 141, whichever is smaller] to Day 196
Week 32	Day 225	Day 197 to Day 252
Week 40	Day 281	Day 253 to Day 308
Week 48	Day 337	≥ Day 309

- a. Target day is equal to the target week×7 days + 1 day.
- b. Treatment switch day = day of the first dose of treatment switch at Week 16 (ie, treatment switch day = treatment switch date – date of the first dose +1), where treatment switch date is taken from the Oral Dosing CRF, as the start date in the first entry of the dosing log for the period of Week 16 to Week 24.
- c. All the data collected on treatment switch day will be counted in ≤ Week 16 except for the AE data. Any new treatment emergent AE occurred on the day of treatment switch will be counted in ≥ Week 24.

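### The Baseline to Week 48 adverse-event display pools placebo and tofacitinib time in the switch arm's column, with no exposure denominator, so that column represents neither treatment

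*SAP*

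**What the plan says.** SAP 6.6.1 names the adverse-event displays: "AEs will be displayed by two analysis periods: (1) Baseline to Week 16; and (2) Baseline to Week 48". The second period includes follow-up. Treatment emergence is counted from the first dosing day and is not reset at the switch. Risk ratios for Tier-2 events are confined to the first period.

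The treatment tables in the Protocol Summary and Protocol 5.1 describe the second sequence as "Placebo BID for 16 weeks followed by open-label 5 mg BID tofacitinib for 32 weeks". SAP 5.2 says that this arm "will advance from placebo to open-label treatment of tofacitinib 5 mg BID at Week 16", and gives it one label up to Week 16 and another afterwards. The Baseline to Week 48 AE period spans both labels.

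SAP 9.4 already contains what is needed to separate the two phases. Table 5 footnote b derives the switch day from the dosing record. Footnote c sets the AE cut: "Any new treatment emergent AE occurred on the day of treatment switch will be counted in" the Week 24 and later side.

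The SAP names no AE display for the time after the switch and no exposure-adjusted AE rate. The version history shows that this is a decision: the entry for version 4 begins "Removed adverse event analyses for the incremental period: Week 16 to Week 48 as" and gives as its reason that "analyses for Baseline to Week 16 and Baseline to Week 48 are sufficient". I cite it only to show intent, not as an inconsistency.

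**The concern.** An event that begins on placebo in Week 10 and one that begins on tofacitinib in Week 30 count alike in the switch arm's Week 48 column. A subject who stops placebo before Week 16 and never takes tofacitinib can also remain in it, because SAP 9.1 analyses safety data regardless of discontinuation.

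Period 2 is the only named AE display that reaches the open-label phase. Protocol 1.2.3.2 lists serious infection and herpes zoster among the risks of tofacitinib, and Amendment 3 added VTE risk checks that the Schedule of Activities places at Week 32 and later. Readers will look to this table for such events and will compare its two columns. That comparison is not tofacitinib against placebo, nor is it two groups on tofacitinib. Without person-time, the table also cannot give a tofacitinib incidence from the half of the trial that starts the drug at Week 16.

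**Working it through.** **Inputs.** The Protocol Summary gives "a 16-week double-blind treatment period, a 32-week open-label treatment period and a 28 day follow-up period", and for size "Approximately 120 subjects per arm will be randomized". The documents give no AE rates. The tofacitinib/placebo rate ratio R (1.5 to 3) and the 16-week placebo risk p (1% to 50%) are therefore assumptions, as are constant rates and no dropout.

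**The plan's own figure.** There is no planned AE figure to reproduce. The stated duration of about 56 weeks does reproduce: 30/7 + 16 + 32 + 28/7 = 56.3 weeks. The exposure lengths below are therefore the plan's.

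**Placebo share of the mixed column.** 16/48 = 33%, or 16/52 = 31% if four weeks of follow-up are counted.

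**Contrast in rates.** Set the placebo rate to 1. The switch arm's average rate over 48 weeks is (16 + 32R)/48. The continuous arm's rate is R.

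| True R | Switch-arm average | Ratio between columns |
|---|---|---|
| 1.5 | 64/48 = 1.333 | 1.5/1.333 = 1.13 |
| 2 | 80/48 = 1.667 | 2/1.667 = 1.20 |
| 3 | 112/48 = 2.333 | 3/2.333 = 1.29 |

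Counting the four follow-up weeks at the tofacitinib rate, (16 + 36R)/52, the ratios become 1.11, 1.18 and 1.26.

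**Crude percentages.** The SAP commits to no rate, so the table as specified would be read in percentages of subjects. Under constant hazards:
- continuous tofacitinib, 16 weeks: 1 − (1 − p)^R
- continuous tofacitinib, 48 weeks: 1 − (1 − p)^(3R)
- switch arm, 48 weeks: 1 − (1 − p)^(1 + 2R)
- switch arm, 32 weeks after the switch only: 1 − (1 − p)^(2R)

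With R = 2:

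| p | Week 16 risk ratio | Continuous, 48 wk | Switch arm, 48 wk | Ratio | Switch arm, after switch only |
|---|---|---|---|---|---|
| 1% | 1.99 | 5.9% | 4.9% | 1.19 | 3.9% |
| 5% | 1.95 | 26.5% | 22.6% | 1.17 | 18.5% |
| 20% | 1.80 | 73.8% | 67.2% | 1.10 | 59.0% |
| 50% | 1.50 | 98.4% | 96.9% | 1.02 | 93.8% |

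Two distortions run in different directions. Compared with the continuous column, the mixed column narrows the contrast. Taken as the percentage with an event on tofacitinib after the switch, it is too high (22.6% against 18.5% at p = 5%). With R = 2, a share of 16/(16 + 64) = 20% of the events in the mixed column arise on placebo.

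**Exposure at stake.** Patient-years = 120 × weeks × 7/365.25.
- Placebo phase, 16 weeks: 36.8
- After the switch, 32 weeks: 73.6
- Continuous tofacitinib, 48 weeks: 110.4
- All tofacitinib: 73.6 + 110.4 = 184.0

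As specified, 74 of these 184 tofacitinib patient-years contribute to no unmixed tofacitinib AE rate.

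**The case against.** The case for leaving the plan alone has substance. The randomised comparison of tofacitinib with placebo is the Baseline to Week 16 display, which is unmixed and carries the Tier-2 risk ratios. The continuous arm is on tofacitinib throughout, so an undiluted long-term column is shown. Protocol 9.3 makes safety descriptive, and nothing is tested on the longer period. Laboratory, ECG and vital-sign summaries are by visit, so they do show the time after the switch. Adjudication committees and the E-DMC review safety separately. The post-switch AE period was dropped on purpose, after blinded data review and with a stated reason.

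The two displays are also nested, so subtraction recovers something. At p = 5% and R = 2, 22.6% − 5.0% = 17.6% of subjects have a first onset after the switch. Dividing by the 95% event-free at Week 16 gives 18.5%, the post-switch risk itself. At p = 1%, 4.9% − 1.0% = 3.9%, which already matches.

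All of this limits the damage, and it rules out treating the matter as a threat to the trial's safety conclusion. It does not show that the two periods suffice. Subtraction yields first-onset subjects only. It gives no person-time and misses events that recur after the switch in subjects who already had one on placebo.

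The sponsor's reporting standards, to which SAP 6.6 defers, are not among the documents and may add displays. The SAP does not commit to any, so the point is that no exposure denominator is specified, not that none will be produced.

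**Conclusion.** The point holds as a reporting weakness. The switch arm's Baseline to Week 48 column represents neither treatment. A descriptive contrast with continuous tofacitinib is attenuated to 1.13, 1.20 or 1.29 for assumed true rate ratios of 1.5, 2 or 3, under constant rates over 48 weeks. The crude percentage overstates what happened on tofacitinib after the switch. The direction holds for any true ratio above 1. The size depends on assumed rates, since the documents give none.

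A reader might infer two stronger conclusions that the documents do not support. One is that the display dilutes any tofacitinib risk. It does not, because the Week 16 comparison and the continuous tofacitinib column contain no mixed exposure, and no inference is drawn from the mixed column. The other is that the switch arm yields no usable tofacitinib figure. Subtracting the nested tables gives first-onset subjects after the switch, which is close to enough for rare events. What is missing is narrower: person-time, repeat events and a clean incidence rate. This is a cheap improvement, not a flaw that endangers a conclusion.

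**What to change.** Keep both existing periods, since the display by randomised sequence has its own use. Add to SAP 6.6.1 a summary of all AEs, SAEs and Tier-1 events by treatment at onset, in two columns:
- placebo exposure, from first dose to switch
- all-tofacitinib exposure, from the first tofacitinib dose in either sequence

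Report subjects with events, patient-years and incidence per 100 patient-years. Take the switch date from Table 5 footnote b and the rule for switch-day events from footnote c. Use the date itself rather than the edge of the visit window, because SAP 9.4 sets that edge to Day 140 when the switch day falls before Day 99, after Day 140 or is missing. State how time after the last dose is counted.

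State also that the all-tofacitinib summary is descriptive and not a randomised comparison: it pools blinded with open-label time, and subjects who start the drug at different points in the study.

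The cost is one more set of safety tables from variables already derived. No new data are needed, and the Baseline to Week 16 analysis does not change.

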6.6.2. Laboratory Data

For laboratory tests, 12-lead ECG parameters and vital signs, these summaries include categorical tables (eg, normal, high, low), and descriptive statistics for change or percent change (for fasting lipids) from Baseline by treatment group and visit. For the FACS, the endpoints to be summarized, which are subsets of lymphocytes and are measured at Baseline, Week 4, Week 16, Week 32, and Week 48, are as follows: CD3+(%, abs), CD3+CD4+(%, abs), CD3+CD8+(%, abs), CD19+(%, abs), CD56+/CD16+(%, abs). Raw values as well as percent change from Baseline will be summarized with descriptive statistics by treatment group and visit.

The number and percent of subjects reporting specific past and present medical histories at screening will be summarized by medical history reporting term (from MedDRA) and treatment group following CaPS.

Clinical findings on any physical examination during the study will be tabulated by treatment group following CaPS.

Previous and concomitant medication usage by medication type will be tabulated by treatment group using the WHO-Drug dictionary following CaPS.

7. INTERIM ANALYSES

No formal interim analysis will be conducted for this study. The analysis of the primary endpoint, key secondary endpoint and other Type I error controlled secondary endpoints conducted at Week 16 is the final analysis (ie, Week 16 analysis) for these endpoints. The E-DMC will be responsible for ongoing monitoring of the safety of subjects in the study according to the charter. The recommendations made by the E-DMC to alter the conduct of the study will be forwarded to Pfizer for final decision. Information about the E-DMC can be found in the E-DMC Charter, which outlines the operating procedures of the committee, including specific description of the scope of their responsibilities, including a plan where communication timelines are defined.

The final analysis (ie, Week 48 analysis) will be performed at the official database release.

9. APPENDICES

9.1. Data Set Description: On-Drug vs. On-Study Data

If for any reason, when subjects have prematurely and permanently discontinued the investigational product (ie, tofacitinib or placebo) during the course of the study, every effort will be made by the study sites and investigators to engage these subjects to follow through the remaining planned study visits and to collect both efficacy and safety data through the end of the study while they are off-drug. It is important that subjects are still blinded to the treatment they receive through the end of the study. For a subject who prematurely discontinues the investigational product (ie, tofacitinib or placebo), the date of the permanent drug discontinuation as recorded on the Disposition – End of Treatment CRF page will be used to separate the efficacy data collected in visits on or before this date as this subject's on-drug data and data collected in visits after this date as this subject's off-drug data.

Because of this data differentiation, there will be two different datasets included for analyses. The first dataset, referred to as On-Drug Data, includes only data that are collected in visits on or before the permanent drug discontinuation. The second dataset, referred to as On-Study Data, includes both the data collected in visits on or before as well as visits after the permanent drug discontinuation. Data that are collected during the on-drug period will be flagged as on-drug data and data collected during the off-drug period will be flagged as off-drug data. Therefore, both on-drug and off-drug data constitute the on-study data. All of the analyses specified in this SAP will use the On-Drug Data unless otherwise specified when using the On-Study Data. The On-Study data will only be used for specific supportive analyses of the primary endpoint (ASAS20), key secondary endpoint (ASAS40) and their 4 components (see [Section 2.1](#), [Section 6.1.2](#) and [Section 6.2](#)) as well as other Type I error controlled secondary endpoints.

All safety data will be analyzed regardless of investigational product discontinuation.

